8.2 SELECTION OF STUDY POPULATION

The study population of this phase I trial will consist of relapsed or refractory AML patients who meet all of the inclusion criteria and none of the exclusion criteria, providing written informed consent.

8.2.1 Inclusion criteria

Inclusion criteria will be evaluated during Screening Period, with the exception of inclusion criteria 3 and 4, which will be evaluated at Visit 1/Day 1; inclusion criteria 5 and 6 will be re-evaluated prior to the first study drug administration (Visit 1/Day 1).

- 1. Male or female patients aged \geq 18 years.
- 2. Documented definitive diagnosis of AML (according to World Health Organization (WHO) criteria, 2008) that is relapsed /refractory to standard treatment, for which no standard therapy is available or the patient refuses standard therapy. For the purpose of this study, refractory AML is defined as following:

Failure to achieve CR/CRi (IWG criteria, 2003) following at least 1 cycle of cytotoxic chemotherapy (or hypomethylating agents if unsuitable for cytotoxic chemotherapy) and unlikely, as per Investigator's judgement, to achieve CR/CRi with further cytotoxic chemotherapy (or hypomethylating agents if unsuitable for cytotoxic chemotherapy).

- 3. WBC count \leq 10 x 109/L at Visit 1; hydroxyurea is allowed to lower WBC count.
- 4. ECOG performance status of 0 to 2 at Visit 1/Day 1.
- 5. Life expectancy of at least 2 months.
- 6. Adequate renal and hepatic laboratory assessments:
 - AST, ALT, ALP $\leq 3.0 \times$ ULN, unless considered due to leukemic organ involvement.
 - Total Bilirubin $\leq 2.0 \times ULN$.
 - Serum creatinine $\leq 2.0 \times \text{ULN}$.

- 7. A female of childbearing potential may be enrolled providing she:
 - has a negative pregnancy test during screening period and
 - is routinely using an effective method of birth control that both results in a Pearl index < 1 and is considered highly effective as defined by the Clinical Trial Facilitation Group (e.g. combined estrogen and progestogen containing hormonal contraception, associated with inhibition of ovulation, intrauterine device, total sexual abstinence or bilateral tubal occlusion) until 6 months from the last study drug administration
 - undergoes a monthly pregnancy test until 6 months from the last study drug administration.
- 8. Able to give written informed consent before any study related procedure.

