- In case of grade 3 or 4 cytokine release syndrome (CRS), it is recommended to consider the use of high dose corticosteroids. Intensive care supportive therapy should be considered for severe or life-threatening CRS, tumor lysis syndrome and/or disseminated intravascular coagulation.

Moreover, in order to independently assess the safety of the "*ramp-up*" schedule of administration, during both its dose escalation and cohort expansion steps, an iDSMB is implemented. The iDSMB, made by independent AML experts, will review patients' data at the end of each dose escalation

cohort, and will take-over the same applicable roles and responsibilities previously assigned to the Cohort Review Committee. The iDMSB will review the safety, efficacy and PK data collected with the *"ramp-up"* schedule, and the Sponsor will follow the iDSMB recommendation for any dose escalation decision.

Although neither complete nor partial responses have been documented so far in the ARMY-1 study, four patients – two of whom treated at the MTD dose level identified with the "*one-shot*" schedule of administration, namely 1.7 mg/kg – showed signs of a treatment-induced TLS, which represents a potential sign for potent antileukemic activity. Overall, these data support to continue the investigation of the clinical activity of MEN1112 given as single agent in AML patients with relapsed/refractory disease, and to investigate the new administration schedule ("*ramp-up*") aiming at exploring additional dose levels in the ARMY-1 study following the iDSMB recommendation for any dose escalation decision.

Therefore, considering a) the fair tolerability of MEN1112 at the MTD dose level (1.7 mg/kg) identified using the "one-shot" schedule, b) the possibility to further increase the MTD dose level by the mean of the new "ramp-up" schedule, c) the implementation of an iDSMB, as well as d) the potentially promising antitumour activity of MEN1112 (as proven by the four reported TLS cases, two of which at the 1.7 mg/kg dose level using the "one-shot" schedule), and eventually e) its potential use in combination studies using the "ramp-up" schedule of administration, the risk-benefit is assessed to be in favour of continuing MEN1112 clinical investigation and development as above described.

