8.2.2 Exclusion criteria

Exclusion criteria will be evaluated during Screening Period, with the exception of exclusion criteria 6, 7, 8 and 9, which will be evaluated at Visit 1/Day 1; exclusion criteria 4 and 5 will be re-evaluated prior to the first study drug administration (Visit 1/Day 1).

- 1. Acute promyelocytic leukaemia (FAB M3 classification).
- 2. Active central nervous system involvement.
- 3. Haematopoietic stem cell transplantation (HSCT) performed within 3 months prior to Screening Period. Patients with prior allogeneic HSCT performed more than 3 months prior to Screening Period are eligible with Medical Monitor approval.
- 4. Active infection requiring intravenous antibiotics.
- 5. Life-threatening illnesses other than AML, uncontrolled medical conditions or organ system dysfunction which, in the investigator's opinion, could compromise the patient's safety or interfere with the patient's ability to comply with the study activities.
- 6. Anti-tumour therapy within 14 days of study Visit 1, excluding hydroxyurea.
- 7. Prior participation in an investigational study (procedure or device) within 21 days of study Visit 1.
- 8. Major surgery within 28 days of study Visit 1/Day 1.
- 9. Radiotherapy within 28 days prior to study Visit 1 or scheduled along the study conduct.
- 10.Known history of HIV or active infection with HCV or HBV.
- 11.Known hypersensitivity to MEN1112 excipients.
- 12.Other active malignancies. History of malignancy in the last 12 months (except for basal cell or squamous cell skin cancer or carcinoma in situ of the cervix or breast or non-melanoma skin cancer).
- 13.Pregnant or breast-feeding women.

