8.5 STUDY PROCEDURES AND ASSESSMENTS

8.5.1 Study Procedures

Approximately 40 study visits are scheduled for screening, treatment and for assessment of safety, efficacy and pharmacokinetics as depicted in the study flow chart (see §2.2) and summarised below. The End of Study Visit is scheduled 180 days after Visit 1/Day 1.

Written Informed Consent has to be obtained PRIOR to performing any study assessment, as described below:

Screening Period (Day -7 to 0)

- Check of Inclusion/Exclusion Criteria
- Demographic data collection
- Medical and medication general history
- AML history, i.e. date of onset of AML, relapsed or refractory status following the last AML treatment, de novo or secondary AML status, number and category of previous AML treatments (including autologous and allogeneic HSCT), and duration of last CR (for relapsed patients), and disease features when available (i.e. AML karyotype, NPM1 and/or FLT3-ITD mutational status, FAB subtype)
- Physical examination, including vital signs (i.e. blood pressure [BP], heart rate [HR], breathing rate [BR], body temperature [T])
- Weight measurement
- Performance Status (PS) evaluation
- 12-lead ECG
- Blood sampling and urine collection for safety lab tests, including pregnancy test (if applicable)
- Blood sampling for anti-HIV antibodies, anti-HBcAg antibodies, HBV-DNA, HCV-RNA
- •

- Blood sampling for immunogenicity assessment
- -
- Bone marrow aspirate for morphologic assessment,
- Recording of AEs and change in concomitant medication

NOTE: Results of laboratory tests for anti-HIV antibodies, anti-HBcAg antibodies, HBV-DNA, HCV-RNA which have been performed within 3 months prior to Screening Period in the context of the standard patient's management (either in the local lab or in a different lab, provided that they comply with local standard procedures) can be reported in the e-CRF under Screening Period procedures and added in the patient file as source documents. In such case, there is no need to repeat the above mentioned tests.

TREATMENT PHASE

CYCLE 1

Visit 1/Day 1, first 3-day "ramp-up" dose

Prior to study drug administration

- Re-check inclusion/exclusion criteria and confirmation of patient's eligibility prior to start treatment
- Physical examination, including vital signs
- Weight measurement
- PS evaluation
- 12-lead ECG
- Blood sampling and urine collection for safety lab test NOTE: Check that WBC count is ≤ 10 x 10⁹/L; hydroxyurea is allowed to lower WBC count.

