8.5.4.2 Secondary Endpoints

- Immunogenicity Evaluation Criteria: Incidence of anti-MEN1112 autoantibodies.
- Clinical Evaluation Criteria:
 - Complete remission (CR) rate at any time point, where CR is defined as: bone marrow blasts <5%, absence of extramedullary disease, absolute neutrophil count >1 x 10⁹/L and platelet count > 100 x 10⁹/L.
 - Composite complete remission (CRc) rate at any time point, defined as the proportion of patients having either CR or CRi (where CRi is defined as: all criteria for CR except residual thrombocytopenia [platelets <100 x 10⁹/L] and/or neutropenia [absolute neutrophil count <1 x 10⁹/L]).
 - Best response rate, defined as the best observed response at any time point between CR, CRi and partial remission ([PR]: all haematologic criteria for CR with bone marrow blasts 5-25% and decrease of pre-treatment bone marrow blast percentage by at least 50%).
 - Duration of CRc: number of days between the date of CR/CRi achievement and the date of the last assessment confirming CR/CRi.
 - Overall Survival (OS), defined as the number of days between the first study drug administration and death from any cause.
 - Correlation of baseline characteristics with clinical activity of MEN1112.

- Incidence, severity, seriousness and treatment related causality of Treatment Emergent Signs and Symptoms (TESSs).
- Frequency of clinically significant abnormalities in physical examination, safety laboratory tests, vital signs and 12-Lead ECG.

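### Relapse is undefined and CR/CRi has no baseline condition, so a relapsed patient whose marrow is already below 5% blasts at screening could enter and be counted as a responder

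*Combined protocol and SAP*

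**What the plan says.** **Entry.** Section 8.2.1, criterion 2, admits AML "that is relapsed /refractory to standard treatment, for which no standard therapy is available or the patient refuses standard therapy". It then opens a definition with "For the purpose of this study, refractory AML is defined as following". That definition covers refractory disease only: "Failure to achieve CR/CRi (IWG criteria, 2003) following at least 1 cycle of cytotoxic chemotherapy" (or hypomethylating agents where chemotherapy is unsuitable), together with the investigator's judgement that CR/CRi is unlikely with more of the same. Relapse is defined nowhere, and neither section 8.2.1 nor 8.2.2 sets a marrow blast minimum.

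**Washout.** Section 8.2.2 excludes "Anti-tumour therapy within 14 days of study Visit 1, excluding hydroxyurea", and "Prior participation in an investigational study (procedure or device) within 21 days of study Visit 1".

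**Baseline marrow.** Section 8.5.1 lists "Bone marrow aspirate for morphologic assessment" in the screening period (Day -7 to 0). No eligibility criterion refers to its result.

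**Response.** Section 8.5.4.2 defines CR by marrow blasts under 5%, no extramedullary disease, and neutrophil and platelet thresholds. CRi is "all criteria for CR except residual thrombocytopenia" and/or neutropenia. Both rates are taken at any time point. PR alone refers to the pre-treatment blast percentage, of which it requires at least a halving.

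**Analysis set.** The efficacy population in section 9.2 requires completion of Cycle 1 and a post-cycle blood test and marrow. It has no condition on disease at baseline.

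**The concern.** A response rate credits a drug with remissions only if the patient was not in remission at the start. Here the lesser response, PR, is tied to baseline and the greater ones, CR and CRi, are not. A patient who enters below 5% blasts and stays there would be scored as a responder at the first on-study marrow (Day 4) or at the post-cycle marrow (Day 22), whatever MEN1112 did.

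The endpoints exposed are CR rate, CRc rate, best response, duration of CRc, and the correlation of baseline characteristics with activity. In the last of these, low baseline blasts would appear to predict response. They are secondary, but they are the protocol's formal response measures. Section 6.3 reports "Although neither complete nor partial responses have been documented so far in the ARMY-1 study" and points to four tumour lysis cases as a sign of activity. Against that background a single artefactual CRi would be the drug's first recorded response. Section 6.3 also has the iDSMB reviewing efficacy data.

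**Working it through.** There is no planned response rate to reproduce: section 9.1 makes no formal sample size calculation, and section 9.3.2 limits efficacy analysis to description. The check is a reading of the rules, followed by arithmetic for scale.

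**Step 1. Can a patient below 5% blasts enter?**

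| Route | Rule that applies | Result |
|---|---|---|
| Refractory, no extramedullary disease | Criterion 2 needs failure to reach CR/CRi and a judgement that it is unlikely with further treatment | Closed: under 5% blasts without extramedullary disease is the marrow state of CR or CRi, so this patient has reached it |
| Either status, extramedullary disease present | Entry possible | Cannot score CR/CRi while that disease persists |
| Relapsed earlier, marrow cleared by salvage therapy that ended more than 14 days before Visit 1 | Relapse undefined, no blast minimum, washout satisfied | Open: no written rule excludes this patient |

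**Step 2. How recent can the earlier treatment be?** Suppose it ended 15 days before Visit 1. The earliest screening marrow is on Day -7, which is 8 days before Day 1 because the protocol numbers a Day 0. So 15 - 8 = 7: the baseline marrow can fall about a week after the last earlier treatment.

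**Step 3. Does anything later remove the patient?** The CR and CRi definitions contain no baseline clause, and neither does the efficacy population. The patient therefore stays in the numerator.

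**Step 4. Scale.** Inputs:
- Up to about 30 expansion patients (section 9.1).
- 47 treated, of whom 22 were in the efficacy population at the data cut-off (Table 1, section 6.2.4.1): 22/47 = 46.8%, as the table states.
- The number of affected patients, x, is not in the documents. I assume 1 to 3.

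Exact (Clopper-Pearson) 95% limits are: lower = 2.5% quantile of Beta(x, n - x + 1); upper = 97.5% quantile of Beta(x + 1, n - x). For x = 0 the upper limit is 1 - 0.025^(1/n).

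| Setting | x/n | Rate | 95% CI |
|---|---|---|---|
| All 30 evaluable, none affected | 0/30 | 0% | 0 to 11.6% |
| All 30 evaluable, one affected | 1/30 | 3.3% | 0.1 to 17.2% |
| All 30 evaluable, three affected | 3/30 | 10.0% | 2.1 to 26.5% |
| 30 x 0.468 = 14 evaluable, one affected | 1/14 | 7.1% | 0.2 to 33.9% |
| 14 evaluable, three affected | 3/14 | 21.4% | 4.7 to 50.8% |

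In every row the true drug effect is taken as nil.

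**Step 5. Experience so far.** If the statement in section 6.3 refers to the patients in Table 1, it corresponds to 0/47 treated (upper limit 7.5%) and 0/22 in the efficacy population (upper limit 15.4%). No false CR/CRi has been reported. Those patients were, however, enrolled under earlier protocol versions.

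**The case against.** The strongest reply is that the population is clear enough in context. Criterion 2 is in the present tense, and section 8.5.1 records relapsed or refractory status after the last AML treatment. Calling a patient in remission relapsed would be a misreading. This carries weight as to how often it would happen. But a history item is not an eligibility gate, and nothing written enforces the intended meaning.

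A second reply is that section 9.3.1 plans differences and shifts from baseline, so a marrow at 2% before and 2% after would be visible, and the SAP (section 9.5) could still settle the scoring. Visibility is a real safeguard for a careful reader of the tables. It does not take the patient out of the CR or CRc count.

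A third reply is that these endpoints are secondary and descriptive, and no decision threshold depends on them. That is correct and limits the importance of the point.

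Some stronger readings are tempting but not supported:
- A reader might infer that refractory patients can also enter in remission. The definition prevents it: a patient whose marrow cleared on salvage treatment has reached CR/CRi and cannot be called unlikely to reach it.
- A reader might add relapse called on molecular findings alone. The documents describe no such practice; NPM1 and FLT3-ITD status are collected only as history, when available.
- A reader might see a recorded response as an automatic entitlement to more drug. The Follow-up notes in section 8.5.1 commit the sponsor only to consider supply, case by case, with iDSMB recommendation and discussion with the investigator and Medical Monitor.

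**Conclusion.** The point holds for one route: a previously relapsed patient whose marrow is already below 5% at screening, without extramedullary disease. As written, that patient is not excluded and counts as CR or CRi irrespective of drug effect.

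The consequence is limited to the secondary descriptive response endpoints and the baseline correlations. A reader might infer that dose finding is compromised. It is not, because the DLT and MTD definitions in section 8.5.4.1 do not use response. Nor do the documents show that any result to date is contaminated.

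The size is unknown because the frequency of such patients is not given. One patient in 30 moves the rate from 0% to 3.3%. The two intervals overlap heavily, so the harm is less a shift in the estimate than a first response that is not one. The figure assumes all 30 are evaluable; at the evaluability seen so far (about 14 of 30), one patient is 7.1%. This should be corrected, but the trial's primary purpose does not depend on it.

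**What to change.** 1. **Scoring rule (the essential change).** In sections 8.5.4.2 and 9.2, and in the SAP, count CR and CRi only in patients who do not already meet the CR/CRi definition on the screening marrow and blood counts. State whether any such patient stays in the denominator as a non-responder or is left out, use the same rule for every response endpoint, and report how many there were.
2. **Entry definition.** In criterion 2 (synopsis and section 8.2.1), define relapse as at least 5% blasts on the existing screening aspirate, or documented extramedullary disease. This uses the protocol's own CR cut-off.

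**Cost.** No new procedure is needed. The first change alone keeps nobody out of treatment and needs only a few lines of text. The second requires the aspirate to be read before Visit 1, inside a short screening window. A few patients with a just-cleared marrow would not be enrolled, or under the first change would not be counted as responders. If the sponsor does not want to narrow entry to a dose-finding study, the scoring rule by itself removes the false responses.

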8.2.2 Exclusion criteria

Exclusion criteria will be evaluated during Screening Period, with the exception of exclusion criteria 6, 7, 8 and 9, which will be evaluated at Visit 1/Day 1; exclusion criteria 4 and 5 will be re-evaluated prior to the first study drug administration (Visit 1/Day 1).

- 1. Acute promyelocytic leukaemia (FAB M3 classification).
- 2. Active central nervous system involvement.
- 3. Haematopoietic stem cell transplantation (HSCT) performed within 3 months prior to Screening Period. Patients with prior allogeneic HSCT performed more than 3 months prior to Screening Period are eligible with Medical Monitor approval.
- 4. Active infection requiring intravenous antibiotics.
- 5. Life-threatening illnesses other than AML, uncontrolled medical conditions or organ system dysfunction which, in the investigator's opinion, could compromise the patient's safety or interfere with the patient's ability to comply with the study activities.
- 6. Anti-tumour therapy within 14 days of study Visit 1, excluding hydroxyurea.
- 7. Prior participation in an investigational study (procedure or device) within 21 days of study Visit 1.
- 8. Major surgery within 28 days of study Visit 1/Day 1.
- 9. Radiotherapy within 28 days prior to study Visit 1 or scheduled along the study conduct.
- 10.Known history of HIV or active infection with HCV or HBV.
- 11.Known hypersensitivity to MEN1112 excipients.
- 12.Other active malignancies. History of malignancy in the last 12 months (except for basal cell or squamous cell skin cancer or carcinoma in situ of the cervix or breast or non-melanoma skin cancer).
- 13.Pregnant or breast-feeding women.

8.2.3 Withdrawal of patients from therapy or assessment

Participation in the study is strictly voluntary and patients have the right to withdraw from the study at any time without explanation. This will not affect his/her rights for future medical care. Treatment should be discontinued also if this is in the best interest of the patient upon Investigator judgement and/or in case of any of the following:

- Non-compliance of the patient or investigator with the protocol
- Disease progression
- DLTs
- Infusion toxicities requiring permanent treatment discontinuation (see §8.4.7)
- Treatment-related grade 3 not haematological toxicity lasting more than 7 days occurring after the first cycle, excluding common complications of AML (in particular infections, bleedings, fatigue)
- Treatment-related grade \geq 4 not haematological toxicity occurring after the first cycle, excluding common complications of AML (in particular infections, bleedings, fatigue)
- Life threatening related Serious Adverse Event (SAE)
- Patient receives other treatment for AML (including HSCT)
- Occurrence of pregnancy

The Investigator is ultimately responsible for the safety and well-being of the patients and, if at any time during the study it is believed that the constraints of this protocol are detrimental to the patient's health, the patient may be withdrawn from the study.

Withdrawal of a patient must be notified to the study monitor, the reason(s) of withdrawal should be documented in the e-CRF and follow-up should be reported. For patients who withdraw from study, End of Study Visit has to be performed at the time of withdrawal.

If a patient prematurely terminates the study, data already collected will be used and analysed for the purpose of the study. In regard to biological samples already collected, in case of Informed Consent withdrawal, the patient may choose if samples not yet analysed, shall be analysed or destroyed.

8.3 IDENTITY OF THE INVESTIGATIONAL PRODUCT

8.3.1 Description of Investigational Medicinal Product

The drug product MEN1112 5.0 mg/mL concentrate for solution for infusion consists of 10 mL of a

solution containing 5.0 mg MoAB/mL as concentrate for solution for infusion

Composition:

Ingredient	Quality	Function
MEN1112	Internal Specification	API

8.3.2 Packaging, labelling, and storage

The packaging and labelling of IMP will be performed

Primary packaging: The drug product MEN1112 (OBT 357) 5.0 mg/mL concentrate is primary packaged in 20 mL vials

Secondary Packaging: The IMP is provided to the clinical sites in center boxes containing 8 vials and a leaflet detailing the instructions on how to administer the drug product. The IMP center boxes are accompanied with the corresponding batch certificate and the certificates of analysis and the form "Handing over and delivery receipt of Investigational Medicinal Product".

Labelling: Each of the vials (primary packaging) and the IMP center boxes (secondary packaging) are labelled in compliance with the current valid international and corresponding national requirements. The labels of the vials bear the unique vial number. These vial labels have a peel-off section which has to be attached to the corresponding section in the drug accountability log upon dispensing of the IMP at visits. The peel-off part reports the number of the vial and the IMP batch number. The fixed section of the vial label reports the contents of the vial and the instructions how to administer and

store the IMP in the respective national language. The label of the IMP center box is multilingual and reports the contents of the center box (quantity and unique numbers of vials) and the instructions how to administer and store the IMP in the respective national language.

Storage:

. The IMP must be

kept in a secure area, out of reach and sight of children and inaccessible to unauthorised individuals.

